7.8.1.2 Analysis of other significant AEs

Other significant AEs will be reported and summarized according to ICH E3 criterion [\(5\)](#). Thus, AEs classified as ‘other significant’ will include those non-serious adverse events with ‘action taken = discontinuation’ or ‘action taken = dose reduced’.

7.8.1.3 AE summaries

An overall summary of AEs will be presented.

The frequency of patients with AEs will be summarized by treatment, primary SOC and PT. AEs which were defined as secondary endpoints will be summarized separately. AEs will also be reported by intensity according to the maximum Common Terminology Criteria for Adverse Events (CTCAE). Separate tables will be provided for patients with other significant AEs according to ICH E3 [\(5\)](#), adverse events of special interest (AESI), for patients with serious adverse events, for patients with AEs leading to dose reduction, for patients with AEs leading to discontinuation, and for patients with drug-related AEs.

The SOC will be sorted alphabetically, PTs will be sorted by frequency (within SOC). Customized sorting orders may also be used based on trial needs, e.g., SOC sorted by frequency.

For further details on summarization of AE data, please refer to “Handling of missing and incomplete AE dates” [\(2\)](#) and “Analysis and Presentation of Adverse Event data from Clinical Trials” [\(6\)](#).

7.8.1.4 AEs of special interest (AESIs)

The protocol defines the following adverse event as AESI:

- Hepatic injury:
A hepatic injury is defined by alterations of the hepatic laboratory and clinical parameters after randomization as detailed by the removal and stopping criteria in CTP Section 3.3.4.1 and CTP Appendix 10.2.

An independent Adjudication Committee will adjudicate certain hepatic events for the severity and causal relationship with the trial medication. Adjudication assessments will be incorporated to the database. Frequency tables will be provided for the PTs in the specified SMQs of events and for the adjudication endpoints. Tables will be provided for events qualifying for adjudication and then separately the events that were confirmed or non-assessable.

7.8.1.5 User-defined adverse event category (UDAEC)

UDAEC will be summarized by dose group, primary system organ class and preferred term. In summary, Table [7.8.1.5:1](#) provides the definition of UDAECs according to AE category or Standardized MedDRA Query (SMQ).

Table 7.8.1.5: 1 Definition of continuous UDAEC

Category	Safety topic	Definition
UDAEC	Hypotension	Investigator-reported, as a dedicated AE category on the AE eCRF page
UDAEC	Syncope	Investigator-reported, as a dedicated AE category on the AE eCRF page
UDAEC	Acute kidney injury	SMQ 'Acute renal failure', narrow scope
UDAEC	Peripheral edema	SMQ 'Haemodynamic oedema, effusions and fluid overload'
UDAEC	Bleeding	SMQ 'Haemorrhages', narrow scope
UDAE	Liver events	Narrow sub-SMQ 'Liver related investigations, signs and symptoms', narrow sub-SMQ 'Cholestasis and jaundice of hepatic origin', narrow sub-SMQ 'Hepatitis, non-infectious' and narrow sub-SMQ 'Hepatic failure, fibrosis and cirrhosis and other liver damage-related conditions'

Summary of hypotension and syncope will be presented for both patient-based and event-based analyses.

Analysis on hypotension based on baseline BP and the lowest BP during the episode will be carried out. Criteria for significant (vs. non-significant) hypotensive episode are:

- Baseline SBP \leq 140: decrease $\left(\frac{\text{lowest SBP during the episode} - \text{baseline SBP}}{\text{baseline SBP}} \right) \geq 30\%;$
- Baseline SBP $>$ 140: decrease $\left(\frac{\text{lowest SBP during the episode} - \text{baseline SBP}}{\text{baseline SBP}} \right) \geq 40\%;$
- Or lowest SBP during the episode $<$ 90.
- Baseline DBP \leq 70: $\left(\frac{\text{lowest DBP during the episode} - \text{baseline DBP}}{\text{baseline DBP}} \right) \geq 30\%;$
- Baseline DBP $>$ 70: $\left(\frac{\text{lowest DBP during the episode} - \text{baseline DBP}}{\text{baseline DBP}} \right) \geq 40\%;$
- Or lowest DBP during the episode $<$ 50.
- Lowest mean arterial pressure (MAP = DP + 1/3(SP – DP)) during the episode $<$ 70.

The severity of hypotension will be categorised based on the CTCAE grades collected from the eCRF:

- CTCAE grade 1 – mild
- CTCAE grade 2 – moderate
- CTCAE grade 3, 4 or 5 – severe

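### SAP 7.8.1.5 prints the percentage limits for a significant hypotensive episode with the sign reversed; the two diastolic lines literally ask for a rise

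*SAP*

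**What the plan says.** SAP 7.8.1.5 announces the classification with "Analysis on hypotension based on baseline BP and the lowest BP during the episode will be carried out" and introduces the list with "Criteria for significant (vs. non-significant) hypotensive episode are". The list has three blocks.

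- **Systolic (SBP).** For baseline up to 140, and for baseline above 140, the word *decrease* is followed by a bracketed ratio, (lowest − baseline)/baseline, to be at least 30% and 40% respectively. An alternative follows: "Or lowest SBP during the episode" below 90.
- **Diastolic (DBP).** For baseline up to 70, and for baseline above 70, the same ratio is to be at least 30% and 40%, this time without the word *decrease*. In the extracted typesetting code the second line reads "70: $\left(\frac{\text{lowest DBP during the episode} - \text{baseline DBP}}{\text{baseline DBP}} \right) \geq 40" (per cent). An alternative follows: "Or lowest DBP during the episode" below 50.
- **Mean arterial pressure (MAP).** The lowest value is below 70, with MAP computed as DBP plus one third of the pulse pressure.

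No absolute-value sign, reversed numerator or negative limit appears. Neither the rest of the SAP nor the protocol restates or corrects the definition. The word *or* stands inside the systolic block and inside the diastolic block. Nothing says how the three blocks are joined.

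**The concern.** This is an operative rule that a programmer has to code, and SAP Section 3 presents the document as the detailed procedure for carrying out the analysis. In all four lines the printed numerator has the wrong order for measuring a fall. Because the systolic and diastolic lines are worded differently, two programmers could reasonably produce different code: one might treat systolic as a fall and diastolic literally, the other might code all four literally.

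The percentage limits exist to catch large relative falls that stop short of the absolute limits, which mainly concerns patients with higher baseline pressure. The blood pressure criterion in Protocol 3.3.3 excludes low pressures only, so it does not keep such patients out. Protocol Table 1.4.2: 1 puts hypotension and orthostatic dysregulation first among the drug's risks, and Protocol 3.2 calls orthostatic dysregulation dose-limiting. A split that drops these episodes from the significant class errs towards understating the risk.

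**Working it through.** The plan gives no figure to reproduce here. All thresholds come from SAP 7.8.1.5. The blood pressure values are illustrations, in mmHg.

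**Step 1: the printed ratio applied to falls that sit on or beyond the limits.**

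| Parameter | Baseline → lowest | Printed: (lowest − baseline)/baseline | Reversed: (baseline − lowest)/baseline | Limit |
|---|---|---|---|---|
| SBP | 140 → 98 | −30.0% | 30.0% | 30% |
| SBP | 150 → 90 | −40.0% | 40.0% | 40% |
| DBP | 70 → 49 | −30.0% | 30.0% | 30% |
| DBP | 90 → 54 | −40.0% | 40.0% | 40% |

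If the lowest value is below baseline, the printed ratio is below zero and cannot reach +30% or +40%. To be met literally, the lowest value must be at least 1.3 or 1.4 times baseline. At baseline DBP 90 that means a lowest value of 1.4 × 90 = 126 or more.

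A check over whole-number pairs with lowest not above baseline gave the same answer. With baseline SBP 90–200 and lowest from 40, 0 of 11,766 pairs meet the printed form and 5,868 meet the reversed form. With baseline DBP 50–120 and lowest from 20, the counts are 0 and 2,369 of 4,686. These count grid points and say nothing about patient frequencies.

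**Step 2: where the percentage lines add something to the absolute limit on the same parameter.**

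- Baseline DBP up to 70: a 30% fall leaves at most 0.7 × 70 = 49, already below 50. This line adds nothing, with or without the sign error.
- Baseline DBP above 70: a 40% fall that leaves at least 50 needs a baseline of 50/0.6 = 83.3, so 84 or more.
- Baseline SBP up to 140: a 30% fall that leaves at least 90 needs a baseline of 90/0.7 = 128.6, so 129–140, with a lowest value of 90 to 0.7 × 140 = 98.
- Baseline SBP above 140: a 40% fall that leaves at least 90 needs a baseline of 90/0.6 = 150 or more.

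**Step 3: what the MAP limit then removes.** Taking the lowest SBP and DBP from one reading, MAP = DBP + (SBP − DBP)/3. To stay at 70 or above:

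- lowest SBP 90 needs DBP of at least 60: 60 + 30/3 = 70;
- lowest SBP 98 needs DBP of at least 56: 56 + 42/3 = 70;
- lowest DBP 50 needs SBP of at least 110: 50 + 60/3 = 70.

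The zones in Step 2 are therefore cut down, but not emptied.

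**Step 4: two episodes that fall through, if any one criterion is enough.**

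| Episode | SBP change | DBP change | MAP | Any absolute limit met? | Printed formulas | Reversed formulas |
|---|---|---|---|---|---|---|
| 150/90 → 112/52 | −25.3% | −42.2% | 52 + 60/3 = 72.0 | No | Non-significant | Significant (DBP) |
| 140/80 → 95/60 | −32.1% | −25.0% | 60 + 35/3 = 71.7 | No | Non-significant | Significant (SBP) |

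The first episode is lost through a line that has no word to correct the formula. The second is lost only if the programmer follows the bracket and ignores *decrease*.

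**The case against.** The strongest reply is that this is a notation slip with one sensible reading. The list concerns hypotensive episodes and uses the lowest pressure, and a rule that needs the lowest value to exceed baseline by 30% or 40% makes no sense there. In the systolic lines, a decrease of at least 30% or 40% is a clear rule in words. One of the two unqualified diastolic lines has no effect at all. The MAP limit catches part of what is left. The documents give no baseline blood pressure distribution, so in 78 patients the number of affected episodes may be very small.

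Most of this stands, and it sets the severity. It does not remove the error. The formula is still wrong in all four lines, and the diastolic lines contain nothing that corrects it. It is also possible that absolute-value bars were lost in text extraction, but plain brackets appear in all four lines, so this is unlikely.

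A further point stands in full. The examples assume that meeting any one criterion is enough, and the SAP does not say so across blocks. If a MAP below 70 were required as well, both examples would be non-significant even with the sign corrected.

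A reader might infer that no hypotensive episode could be classed as significant. The documents do not support that: the limits of 90, 50 and 70 do not depend on the sign. A reader might also infer that the hypotension endpoints are compromised. They are not. The secondary endpoints in Protocol 2.1.3 and SAP 5.2.2 use CTCAE grade 3 or higher hypotension or syncope, and discontinuation. Hypotension itself is investigator-reported on the eCRF, and its severity is taken from the CTCAE grade.

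**Conclusion.** The concern holds as an error in four printed formulas, of minor severity. No fall can satisfy the printed expressions. The intent can be recovered from the wording of the systolic lines, but the diastolic lines literally require a rise. The unqualified error has a practical effect only in the line for baseline DBP above 70, from a baseline of about 84 upward. If *decrease* is ignored, the systolic gap covers baseline 129–140 with lowest 90–98, and baseline 150 or more with lowest from 90 to 60% of baseline. In each case this is further limited by the MAP criterion.

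These statements assume that the criteria are joined by *or* and that the lowest SBP and DBP belong to one reading. The number of patients affected cannot be estimated from the documents. At stake is a label in one descriptive safety analysis: no event leaves the adverse event tables, and Protocol 7.1 plans no statistical testing.

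**What to change.** In SAP 7.8.1.5, write all four percentage criteria as (baseline − lowest)/baseline, at least the percentage already stated, and leave every threshold as it is. Word the systolic and diastolic lines alike. Have the sponsor state how the systolic, diastolic and MAP blocks combine.

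SAP version 1.0 is marked final, so the correction should be documented before treatment information is released under SAP Section 8. The definition is then not open to interpretation after unblinding. The cost is four formula lines and one added sentence; no data collection or other analysis changes.

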7.8.2 Laboratory data

The analyses of laboratory parameters will be descriptive in nature and will be based on BI standards (7). Note that data from the central laboratory will be used for all displays described below, unless otherwise specified.

For continuous safety laboratory parameters standardized and normalized values will be derived as well as the differences to baseline. Normalisation means transformation to a standard unit and to a standard reference range. The process of normalisation, handling of repeat values at the same visit for by-visit displays, as well as standard analyses for safety laboratory data are described in the BI guidance for “Handling, Display and Analysis of Laboratory Data” (7). All analyses considering multiple times of the ULN (as described below) will be based on standardised and not normalised values.

Laboratory parameters will be shown in conventional units. Where conventional units differ from SI units, analyses will be repeated on SI units in the appendix.

Laboratory values will be compared to their reference ranges and frequency tables will be provided for the number of patients within and outside the reference range at baseline (see Section 6.7) and the last measurement on treatment. Descriptive statistics will be provided by treatment group for baseline, last value on-treatment and for changes from baseline to last value on treatment. Frequency tables will summarise the number of patients with potentially clinically significant abnormalities.

Only patients with at least one available on-treatment value will be included in the analysis of an individual laboratory parameter. All individual data will be presented in listings.

The following lab parameters will also be presented graphically:

- Haematocrit
- Haemoglobin
- RBC count / erythrocytes
- WBC / leukocytes
- Platelet count / thrombocytes
- Reticulocytes
- INR
- ALT
- Alkaline phosphatase
- AST
- Bilirubin (total)
- Albumin
- gamma-GT
- eGFR

To support analyses of liver related adverse drug effects, the frequency of patients with AST and/or ALT $\geq 3\times$ ULN combined with the total bilirubin $\geq 2\times$ ULN in a 30-day period after AST/ALT elevation will be displayed, stratified by alkaline phosphatase $< 2\times$ ULN and $\geq 2\times$ ULN (a patient can potentially be in both alkaline phosphatase strata in case of multiple AST/ALT and bilirubin elevations). The start of the 30-day time span is triggered by each liver enzyme elevation above defined thresholds. This analysis will be based on standardised laboratory values.

A graphical analysis of the ALT and total bilirubin during the on-treatment period will also be performed; the so called eDISH plot. In the graph, for each subject, the peak total bilirubin is presented as a fold increase over the ULN against the peak ALT as a fold increase over the ULN, on a log 10 scale. The measurements displayed or total bilirubin and ALT may, or may not, occur on the same date. Two reference lines, 2xULN for total bilirubin and 3xULN for ALT, are drawn onto the graph to divide the plane into four quadrants. Normal cases are in the lower left quadrant, potential DILI cases are in the upper right quadrant (Hy's Law quadrant), while the lower right quadrant is known as the Temple's corollary range (ALT $\geq 3\times$ ULN and total bilirubin $< 2\times$ ULN). The same graphical analysis will be repeated on AST and total bilirubin. Details on patients with elevated liver enzymes will be listed.

Clinically relevant findings in laboratory data will be reported as baseline conditions (at screening) or as AEs (during the trial). If judged clinically relevant by the investigator and will be analysed as such.

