Trial Periods	Screening ¹			Randomised Treatment									Follow-Up	
	1a ¹	1b ¹	1c ¹	2 ²	3	4	5	6	7	8	9	10	EoT / ED ³	EoS ³
Week	-6			R	1	2	4	6	8	12	16	20	24	28
Day	-42			1	8	15	29	43	57	85	113	141	169	197
Time window for visits (days)	See footnote 1			N/A	+ 2	+ 2	+ 2	± 3	± 3	± 5	± 5	± 5	± 5	± 5
Fasting status ⁴	NF	F	F	F	NF	NF	F	NF	F	NF	NF	NF	F	F
Informed consent	x													
Register patient in IRT system via IRT call	x													
Demographics ⁵	x													
Medical history / baseline conditions ⁵	x													
Concomitant therapy	x	x	x	x	x	x	x	x	x	x	x	x	x	x
Anthropometric measures ⁶	x			x	x	x	x	x	x	x	x	x	x	x
Vital signs ⁷	x			x ²³	x ²³	x ²³	x ²³	x	x	x	x	x	x	x
Physical examination ⁸	x ²²			(x)	(x)	(x)	(x)	(x)	x	(x)	(x)	(x)	x	(x)
Resting 12-lead ECG ⁷	x			x ²³	x ²³	x ²³	x ²³	x	x	x	x	x	x	x
Safety laboratory sampling	x			x	x	x	x		x	x	x	x	x	x
Pregnancy testing ⁹	x _s			x _u			x _u		x _u	x _u				
Gastroscopy ^{1, 10}		x												
Hepatic venous pressure gradient (HVPG) ^{1, 11}			x						x				x	
Ultrasound (liver and spleen) ^{1, 12}			x				x		x				x	x
Review of in-/exclusion criteria	x	x	x	x										

FLOW CHART contd.

Trial Periods	Screening ¹			Randomised Treatment									Follow-Up	
	1a ¹	1b ¹	1c ¹	2 ²	3	4	5	6	7	8	9	10	EoT / ED ³	EoS ³
Week	-6			R	1	2	4	6	8	12	16	20	24	28
Day	-42			1	8	15	29	43	57	85	113	141	169	197
Time window for visits (days)	See footnote 1			N/A	+ 2	+ 2	+ 2	± 3	± 3	± 5	± 5	± 5	± 5	± 5
Fasting status ⁴	NF	F	F	F	NF	NF	F	NF	F	NF	NF	NF	F	F
Randomisation				x										
IRT call				x	x	x	x	x	x	x	x	x	x	
Dispense trial medication				x	x	x	x	x	x	x	x	x		
Dose-titration ¹⁴				x	x	x								
Train patient (home BP and HR monitoring) ¹⁵				x	(x)									
Home BP and HR monitoring (by patient) ¹⁵				x	→	→	→	→	→	→	→	→	→	→
Biobanking sampling ¹⁹				x					x				x	
PRO completion (EQ-5D-5L, SF-36v2, CLDQ) ²⁰				x									x	
All AEs / SAEs / AESIs ²¹	x	x	x	x	x	x	x	x	x	x	x	x	x	x
Collect trial medication					x	x	x	x	x	x	x	x	x	
Compliance check					x	x	x	x	x	x	x	x	x	
End of trial medication													x	
Completion of patient participation														x

Footnotes:

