
Potential risks associated with the HVPG measurement, which are almost exclusively related to the venous access, usually performed under local anaesthesia and sometimes mild sedation. Common side effects include those associated with procedural sedation (e.g. nausea, vomiting, aspiration pneumonia, irregular heartbeat, breathing difficulties), pain at the insertion site, or slight thoracic or abdominal discomfort when advancing the catheter through the vena cava system into the hepatic vein and while inflating the balloon. Specific but rare complications related to the venous access include haematomas at the access site, pneumothoraces requiring a chest tube and cardiac arrhythmias (R20-3977). Iodinated contrast material (ICM) also has the potential to cause hypersensitivity and can lead to contrast-induced renal injury
	
The HVPG procedure is the gold standard to assess portal pressure quantitatively, but, it is invasive, resource-intensive, and requires interventional skills and expertise in interpreting the reliability and plausibility of pressure readings (refer to Section 5.1.1), hence, the procedure is not commonly performed as part of clinical practice. To date, there are no alternative, non-invasive parameters reflecting the degree of portal pressure with similar accuracy as HVPG. The complication rate of HVPG measurement is low, and the pressure measurement itself is not painful. Patients may be sedated if required (e.g. they are nervous) or based on defined standards. The procedure is performed using ultrasound-guidance, and under fluoroscopic control with use of ionising radiation and ICM. Radiation exposure is, in most cases, very limited and the effective dose received by patients (~ 5.4 mSv) is inferior to most diagnostic radiology examinations of the abdomen and similar to that of a plain X-ray of the upper gastrointestinal tract (R20-4181, R20-4191, R20-3299). The volume of ICM used is in the region of 7 mL (R20-4181)
	
Risks relating to HVPG measurements will be mitigated by placing the trial at sites who are experienced in / have access to a nearby site experienced in the procedure. Such sites will be familiar with preparing patients before the procedure, allaying any fears, and the subsequent patient monitoring that is required. This might include adequate hydration to help avoid e.g. contrast-induced renal injury, and educating patients regarding symptoms suggestive of complications. Patients will be monitored for AEs, and those with contraindications to the procedure will be excluded. The burden of HVPG measurements on the patient will also be reduced as far as possible in terms of the chosen trial design (refer to Section 3.2)

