7.2.6 Safety analyses

Safety analyses will be descriptive in nature and follow BI standards, including (but not limited to): AEs, SAEs and AESI. AEs will be coded using the Medical Dictionary for Drug Regulatory Activities (MedDRA). Standard BI summary tables and listings will be produced. All AEs with an onset between start of treatment and end of the REP (refer to Section [1.2.1](#)) will be assigned to the on-treatment period for evaluation.

[figure not shown]
Safety analyses will be done by “treatment at onset” principle. All treated patients will be included in the safety analysis (TS). In general, safety analyses will be descriptive in nature and will be based on BI standards. No hypothesis testing is planned.

Statistical analysis and reporting of AEs will concentrate on treatment-emergent AEs, i.e. all AEs occurring between start of treatment and end of the REP. AEs that start before first trial medication intake and deteriorate under treatment will also be considered as ‘treatment-emergent’.

Frequency, severity, and causal relationship of AEs will be tabulated by system organ class and preferred term after coding according to the current version of the MedDRA at DBL.

Laboratory data will be analysed both quantitatively as well as qualitatively. The latter will be done via comparison of laboratory data to their reference ranges. Values outside the reference range, as well as values defined as clinically relevant, will be summarised. Treatment groups will be compared descriptively with regard to distribution parameters as well as with regard to frequency and percentage of patients with abnormal values or clinically relevant abnormal values.

Vital signs, physical examinations, or other safety-relevant data observed at screening, baseline, during the course of the trial and at the end-of-trial evaluation will be assessed with regard to possible changes compared to findings before start of treatment.

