6.7 BASELINE, TIME WINDOWS, AND CALCULATED VISITS

Regarding efficacy and safety endpoints, the term “baseline” refers to the last observed measurement prior to administration of any randomized study medication.

Measurements taken prior to the first intake of randomized study medication will be considered pre-treatment values. Pre-treatment values will be assigned to a visit according to the nominal visit number as recorded on the eCRF or as provided by the laboratory.

In general, the date of the first drug administration will be used to separate pre-treatment from on-treatment values. Measurements taken after first trial medication intake will be considered on-treatment values if they have been obtained up to end of the parameter-specific follow-up period as defined in Table [6.1:1](#) below and will be assigned to the randomized study medication for efficacy analyses and to the first study medication taken for safety analyses.

Measurements taken after the end of the endpoint specific follow-up period will be considered post-treatment values.

Table 6.7:1 Endpoint specific follow-up period for the assignment to treatment phase

Endpoint	Last day of assignment to treatment phase (Days after study medication stop date)
Efficacy	
HVPG	8
[REDACTED]	
Safety	
Adverse events	7
Safety laboratory measurements	3
Vital signs (including body weight, blood pressure)	1

For derivation of the last value on treatment, minimum value on treatment, and maximum value on treatment, all values from the relevant phase (whether or not collected in any time window; see Table [6.1:1](#) for definition of the trial phases) will be considered; these will be derived for analysis of laboratory and vital signs data.

On-treatment efficacy, safety [REDACTED] measurements will be assigned to visits based on the extended time windows around the planned visit dates, defined relative to the day of first trial medication intake (see Table [6.7:2](#)).

For the analyses of the secondary and further safety endpoints at week 8, the actual V7 date + X days (X=3 or 7 days for safety laboratory and AE respectively) will be used for the analysis time windows.

Table 6.7:2 Time windows for assignment of measurements to visits for statistical analysis

Visit number /name	Visit label	Planned day	Time window (Days)				
			Window (per CTP)	Start (per CTP)	End (per CTP)	Start (extended) *	End ^A (extended) *
V1	Screening	-42	+7			-∞	0
On-treatment							
V2	Week 0	Day 1	N/A	1	1	≤1	1

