V3	Week 1	Day 8	+2	8	10	2	11
V4	Week 2	Day 15	[contact]
V5	Week 4	Day 29	[contact]
V6	Week 6	Day 43	±3	40	46	37	50
V7	Week 8	Day 57	±3	54	60	51	71
V8	Week 12	Day 85	±5	80	90	72	99
V9	Week 16	Day 113	±5	108	118	100	127
V10	Week 20	Day 141	±5	136	146	128	155
V11	Week 24/ EoT	Day 169	±5	164	174	156	Study medication stop date + X [#] days
Off-treatment							
V12	Week 28/ EoS	Day 197	±5	192	202	Study medication stop date + X [#] days	Day of last follow-up value days +1

^A In case of premature discontinuation of the study medication, an early EoT visit has to be performed within 7 days of medication stop date. If such an EoT Visit falls into the time window of a previous visit, measurements will be assigned to this previous visit and the visit value will be determined as described above. In this case, the time window for the visit that includes the early EoT visit will end X days after the study medication stop date, including Day X. Patients will then be asked to continue in the study according to the visit schedule. Off-treatment measurements will be assigned to visits in the same manner.

Days are counted relative to the day of first treatment, which is defined as Day 1.

* Start (extended): End of extended window of last visit+1

End (extended): Midpoint of planned days between current visit and next visit

#X= 3 days for safety laboratory; X=1 day for biomarkers and vital sign, respectively; X= 8 days for HVPG and Fibroscan data.

The midpoint between two on-treatment visits defines the end of a time window, with the midpoint being included in the time window of the preceding visit. The end of the time window of the last on-treatment visit (end of treatment (EoT)) is endpoint dependent (Table 6.7:1).

Repeated and unscheduled efficacy and safety measurements will be assigned to the nominal visits and listed in the subject data listing according to the time windows described above. Only one observation per time window will be selected for analysis at an on-treatment visit - the value which is closest to the protocol planned visit day will be selected. If there are two observations which have the same difference in days to the planned day, the first value will be selected. If there are two observations on the same day, the first value will be selected. If there

are multiple values within the time window of the last visit, including a value on the last day of drug intake, the value on the last day of drug intake is used as the value of the last visit.

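### SAP 7.8.2 names only last-on-treatment laboratory range and change tables, so a value that leaves the range and recovers counts as normal there, although on-treatment minimum and maximum are already derived

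*SAP*

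**What the plan says.** SAP 7.8.2 names two general table types for safety laboratory parameters.

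- Reference-range frequency tables, which count patients "within and outside the reference range at baseline (see Section 6.7) and the last measurement on treatment".
- Summary statistics: "Descriptive statistics will be provided by treatment group for baseline, last value on-treatment and for changes from baseline to last value on treatment".

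SAP 6.7 defines more than these tables use: "For derivation of the last value on treatment, minimum value on treatment, and maximum value on treatment, all values from the relevant phase" are taken into account, whether or not they fall in a visit window. It gives the purpose too: "these will be derived for analysis of laboratory and vital signs data". The on-treatment period for laboratory data ends shortly after the last dose ("X= 3 days for safety laboratory").

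Protocol 7.2.6 describes the laboratory analysis more broadly: "Values outside the reference range, as well as values defined as clinically relevant, will be summarised". It also plans to compare the arms on the frequency of patients with abnormal values and with clinically relevant abnormal values. It gives no time basis for either. SAP 4 declares no change from the protocol's methods.

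SAP 7.8.2 contains further displays:

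- a frequency table of potentially clinically significant abnormalities, with no time basis stated;
- graphs of 14 parameters;
- a table of ALT/AST elevation combined with bilirubin elevation within 30 days;
- eDISH plots of peak ALT, and of peak AST, against peak bilirubin;
- listings of all individual values.

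It refers to an internal sponsor guidance for its standard laboratory analyses.

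**The concern.** A last-value table favours recovery. A patient whose potassium or creatinine left the reference range at Week 4 and was back inside it at the last on-treatment sample is tabulated the same way as a patient who was never abnormal. The design makes such recovery plausible, since protocol 4.1.4 and 4.1.4.1 allow interruption and down-titration after an adverse event. Patients randomised to active drug stay in their planned arm for safety analyses (SAP 6.4), so a value that recovered after a dose reduction enters that arm's table as normal.

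Protocol 7.2.6 separates plain out-of-range values from clinically relevant ones. The clinically significant abnormality table serves the second category. For the first, the last-value table is the only frequency table that SAP 7.8.2 names. What is at stake is how complete the tabulated comparison of laboratory abnormalities is between two doses and placebo. No efficacy result is touched.

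**Working it through.** The plan gives no figure on this point, so there is nothing to reproduce. The check has three steps.

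**1. Variables derived against variables used**

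| On-treatment quantity | Derived (SAP 6.7) | Display named in SAP 7.8.2 |
|---|---|---|
| Last value | Yes | Reference-range frequency table; summary and change table |
| Maximum | Yes | Peak values in eDISH plots only (ALT, AST, total bilirubin) |
| Minimum | Yes | None named |

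The graph list includes haemoglobin, platelets, INR and eGFR, but not creatinine, sodium or potassium. Creatinine is partly covered through eGFR, which protocol 5.2.3 bases on serum creatinine.

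By-visit tables, if they exist in the internal guidance, would not fully replace a worst-value table. SAP 6.7 keeps one observation per window, the one closest to the planned day. An unscheduled abnormal sample can therefore drop out of a by-visit table, whereas the minimum and maximum use all values in the phase.

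**2. How many samples the tables use**

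In the protocol flow chart, the row "Safety laboratory sampling" is marked after first dose at Visits 3, 4, 5, 7, 8, 9, 10 and EoT, and not at Visit 6. Visit 2 is baseline. That gives k = 8 scheduled post-baseline on-treatment samples for a patient who completes treatment, of which the tables use 1.

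Assume an abnormality that is present at exactly one of the 8 samples, each equally likely:

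share absent from the last-value tables = (k − 1)/k = 7/8 = 87.5%.

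An abnormality that persists to the last sample is not missed at all.

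**3. What a worst-value table does to the counts**

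Let p be the chance that one sample is out of range, independent between samples. Neither p nor independence comes from the documents. The chance of at least one out-of-range value in 8 is 1 − (1 − p)^8. Multiplying by 26 patients per arm gives expected counts.

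| p | Last sample only | At least one of 8 | Expected per 26: last / any |
|---|---|---|---|
| 1% | 1% | 7.7% | 0.26 / 2.01 |
| 2.5% | 2.5% | 18.3% | 0.65 / 4.77 |
| 5% | 5% | 33.7% | 1.3 / 8.75 |
| 10% | 10% | 57.0% | 2.6 / 14.81 |

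Values within a patient are correlated, so the real gap would be smaller. The table shows how much a last-value count can leave out. It also shows how much background a worst-value count brings in, in every arm including placebo.

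**The case against.** The strongest reply is that SAP 7.8.2 is not a complete list of tables. It refers to an internal guidance for standard laboratory analyses and mentions by-visit displays that it does not itemise. SAP 7.8.3 on vital signs also names no minimum or maximum, although SAP 6.7 derives them for that purpose too. Worst-value tables may therefore already be planned. This stands as a possibility, but the documents do not show it, and the last-value rule in 7.8.2 is explicit. If the guidance does contain such tables, one sentence in 7.8.2 would settle the matter.

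Three stronger readings are tempting, and the documents do not support them.

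- **A reader might infer that transient abnormalities go unreported.** They do not. The clinically significant abnormality table carries no last-value restriction. The 30-day ALT/AST–bilirubin table is triggered by each enzyme elevation, and the eDISH plots use peaks. Clinically relevant findings are adverse events (protocol 5.2.3), and events leading to dose reduction have their own table (SAP 7.8.1.3). Acute kidney injury has a dedicated category (SAP 7.8.1.5), 14 parameters are graphed, and all values are listed.
- **A reader might infer that the SAP contradicts the protocol.** Protocol 7.2.6 sets no time basis and does not require the worst value. The SAP is narrower than that wording allows, but not in breach of it.
- **A reader might take contrast exposure at the Week 8 HVPG as a case in point**, since protocol 1.4.2 says that contrast material "can lead to contrast-induced renal injury". The schedule does not support this. The HVPG takes place on the visit day or within seven days (protocol 5.1.1). The next scheduled safety sample after Week 8 (Day 57) is Week 12 (Day 85), 21 to 28 days after the procedure on planned days. After the Week 24 HVPG the next scheduled sample is at EoS, which is off treatment. A short-lived change would usually fall between scheduled samples, where a worst-value table would miss it too. All arms undergo the procedure.

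It is also fair to say that many patients with cirrhosis may be out of range at baseline, for example on platelets, and that worst-value counts add background noise with 26 per arm. That is a reason to present shifts from baseline and to read them against placebo. It is not a reason to tabulate the last value alone.

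**Conclusion.** The point holds for the two table types named in SAP 7.8.2. In them, an out-of-range value that resolves before the last on-treatment sample is counted as within range. For a patient who stops early, the last on-treatment sample is the last one up to 3 days after the last dose.

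Because of the other displays, the practical gap is limited mainly to non-liver parameters, for example creatinine, sodium and potassium, and to values below the clinically significant threshold.

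The use of 1 sample in 8 is a count from the flow chart for a patient who completes treatment. The 7-in-8 figure is an illustration that rests on a single-sample abnormality with equal chances across samples, and it should not be read as the share of abnormalities this trial would miss. Nothing in the documents shows that a safety conclusion would change. This is a cheap improvement.

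**What to change.** In SAP 7.8.2:

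1. Keep the last-value tables.
2. Add, by treatment group, reference-range shift tables from baseline to the on-treatment maximum (upper limit) and minimum (lower limit), using the SAP 6.7 derivation, together with change from baseline to those values.
3. State that the table of potentially clinically significant abnormalities counts any on-treatment value.
4. If the internal guidance already provides item 2, say so and name the tables.

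The change should be made before treatment information is released (SAP 8). It costs a few lines of SAP text and further runs of a planned table on variables already derived, with no new data. The downside is that more patients will be counted as out of range in every arm, so the tables need a note that they are to be read against placebo and alongside the last-value tables.
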